The undersigned confirm that the following protocol has been agreed and approved by the Sponsor and that the Chief Investigator agrees to conduct the trial/study in compliance with this approved protocol and will adhere to the principles of GCP, the Sponsor SOPs, and any other applicable regulatory requirements as may be amended from time to time.

[name]	[name]	
		28 April 2021
Chief Investigator	Signature	Date

LIST OF ABBREVIATIONS

AE	Adverse Event	
API	Application Programming Interface	
BP	Blood Pressure	
CBS	Cambridge Brain Science	
CI	Chief Investigator	
CNORIS	Clinical Negligence and Other Risks Scheme	
CRF	Case Report Form	
CTIMP	Clinical Trial of an Investigational Medicinal Product	
DMS	Data Management System	
eGFR	Estimated Glomerular Filtration Rate	
eCRF	Electronic Case Report Form	
GCP	Good Clinical Practice	
GDPR	General Data Protection Regulation	
GP	General Practice	
НВРМ	Home Blood Pressure Monitor	
ICF	Informed Consent Form	
HTTPS	Hypertext Transfer Protocol Secure	
HRA	Health Research Authority	
ICH	International Council for Harmonisation of Technical Requirements for Pharmaceuticals for Human Use	
ISF	Investigator Site File	
IMP	Investigational Medicinal Product	
MEMO	Medicines Monitoring Unit	
NCTIMP	Non-Clinical Trial of an Investigational Medicinal Product	
NHS	National Health Service	
NICE	National Institute for Health and Care Excellence	
PDF	Portable Document Format	
PI	Principal Investigator	
PIC	Participant Identification Centre	
PIS	Patient Information Sheet	

R&D	Research & Development
REC	Research Ethics Committee
SAE	Serious Adverse Event
SC	Steering Committee
SMG	Study Management Group
SOP	Standard Operating Procedures
SSL	Secure Sockets Layer
TASC	Tayside Medical Science Centre
TMF	Trial Master File

SUMMARY/SYNOPSIS

Study Title	RECALL Pilot - A pilot study to determine the feasibility of a prospective, randomised, double-blind clinical trial of reducing systolic blood pressure to prevent dementia and cognitive decline		
Study Design	Feasibility study		
Study Population	Adults aged 60 or over		
Sample Size	At least 100		
Planned Trial/study Period	approximately 17 months		
Clinical phase duration	n/a		
Follow up phase duration	n/a		
Primary	Objective Determine the feasibility of carrying out a larger trial by testing the recruitment and screening processes in primary care		
Secondary	Objectives Assess suitability of online cognitive testing for study cohort	Outcome Measures Proportion of participants who complete a baseline test	
	Assess baseline cognitive function	Proportion of study population completing online screening cognitive function test and scores obtained	
	Assess feasibility of requiring each participant to identify two individuals who agree to act as alternative contacts Proportion of participants who have two consenting alternative contacts		
	Assess feasibility of home blood pressure monitoring using study supplied HBPM machine	Proportion of participants submitting a complete set of home BP measurements	
	Assess baseline blood pressure suitability of study cohort	Proportion of participants with a home BP submission averaging 140mmHg or below systolic	
	Assess feasibility of using portable i-STAT Alinity device for providing blood results	Proportion of blood results obtained using portable system	

	Assess the likely number of eligible patients signing up	Proportion of those invited who meet proposed formal study entry criteria
Inclusion Criteria	Aged 60 years or over Email address (per participant) and internet access	
Exclusion Criteria	Patients considered unsuitable for invitation (GP opinion) Patients with a medical history of dementia or on treatment for dementia	

1 INTRODUCTION

This protocol describes the methods of a feasibility study to test several aspects of trial methodology (including recruitment, eligibility testing and baseline data collection) as part of the planning for a large-scale online trial of blood pressure lowering to prevent dementia.

2 BACKGROUND & RATIONALE

Dementia is the leading cause of death in the UK and the biggest health and social care challenge of the 21st century. There is no effective treatment available or imminent for the commonest causes, which are Alzheimer's disease and vascular dementia. About half of cases have a significant vascular component. There is evidence that other end-organ damage driven by vascular disease is preventable (for example, cardiac, renal and stroke disease). Primary prevention is therefore also a realistic possibility for dementia.

Complex interventions aiming to slow cognitive decline have been disappointing, are time consuming and labour intensive and require extensive commitment on behalf of the health services, individual therapist, and participant. Mounting evidence supports the beneficial effects of reducing blood pressure to ameliorate cognitive decline and to prevent dementia. We intend to conduct a large online study of blood pressure lowering medication to lower blood pressure and prevent dementia. Although elements of the proposed study methodology have been used in other studies, they have not yet been tested in the target population. We therefore plan a pilot study to assess the feasibility of several aspects of the proposed method.

3 STUDY OBJECTIVES & OUTCOMES

Table 1: Primary Objectives and Outcome Measures

Primary Objective:	Outcome Measure:	Timepoint of outcome measured
Determine the feasibility of carrying out a larger trial by testing the recruitment and screening processes in primary care.	Recruitment numbers Protocol adherence	End of pilot

Table 2: Secondary Objectives and Outcome Measures

Secondary Objective:	Outcome Measure:	Timepoint of outcome measured
Assess suitability of online cognitive testing for study cohort	Proportion of participants who complete a baseline test	n/a
Assess baseline cognitive function	Proportion of study population completing online screening cognitive function test, and scores obtained	n/a
Assess feasibility of requiring each participant to identify two individuals who agree to act as alternative contacts	Proportion of participants who have two consenting alternative contacts	n/a
Assess feasibility of home blood pressure monitoring using study supplied HBPM machine	Proportion of participants submitting a complete set of home BP measurements	n/a
Assess baseline blood pressure suitability of study cohort	Proportion of participants with a home BP submission averaging 140mmHg or below systolic	n/a
Assess feasibility of using portable i-STAT Alinity device for providing blood results	Proportion of blood results obtained using portable system	n/a
Assess the likely number of eligible patients signing up	Proportion of those invited who meet proposed formal study entry criteria	n/a

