4.1.4 Blood Tests

Participants will be asked to have a blood test carried out using the i-STAT Alinity portable system developed by Abbott. This sample will be obtained at either the GP practice, MEMO Research at Ninewells Hospital, a Community hub or other suitable facility (investigator opinion) as necessary. The blood test will involve one draw of venous blood and will provide results for: Sodium, Potassium, Chloride, TCO2, Anion Group, Ionized Calcium, Glucose, Urea Nitrogen (BUN), Creatinine, calculated eGFR, Haematocrit and Haemoglobin

Full working instructions and training will be provided to the Health Care Professional using the i-STAT system.

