4.5 TISSUE

One blood sample will be collected, analysed and discarded at the same visit in this study.

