5.5 IMPACT OF COVID-19 ON STUDY DELIVERY

The study was approved for an additional 9 month's extension by the Sponsor. As a result of the COVID-19 pandemic, study recruitment was paused in March 2020. However, the study website remained open for participants to register and for post consented participants to complete the online assessments. The impact of the COVID-19 pandemic on both the short- and long-term delivery of both standard healthcare and clinical studies within the NHS is unknown. However, in order to eliminate/reduce a potential negative impact of the COVID-19 pandemic on the RECALL Pilot study, a number of mitigation strategies may need to be implemented. These strategies have been designed to: (i) allow the continuation of online recruitment to the study (ii) accommodate participants who would prefer to avoid attending a hospital for completion of the required blood sample (iii) acknowledge the COVID-19 restrictions placed on primary care practices by providing alternative sites for taking blood samples (iv) allow the use of community hubs or other suitable facility for taking blood samples (v) allow the study team to adopt a pragmatic approach to face-to-face study visits whilst following government guidance. This may mean allowing for a delay in obtaining blood samples to ensure participant and staff safety.

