6 DATA COLLECTION & MANAGEMENT

6.1 DATA COLLECTION

A dedicated study eCRF website will be used to collect the study data. This system will be developed by MEMO Research who have experience in such systems for clinical trials. Data entered directly on the eCRF website will be considered to be source data. Caldicott approval will be sought to permit the storage of patient-specific data on the secure study database.

Participant-reported data will be collected by a series of web-based questions, games and tasks, and questionnaires. Participant-reported data will include demographic data, relevant past medical history and family history, concomitant medications, details of two alternative contacts and blood pressure readings. This will be requested at the point of consent, and participants will be given the opportunity to update this during the study.

Patient-reported data will be entered by participants directly.

Participants will be asked to complete various questionnaires to provide feedback on their experience of participating in the study.

Research Nurses will enter the results of the blood test taken using the i-STAT Alinity Device.

Participants may be contacted to request clarification of data points. Any changes to data points will be logged and justified.

Participants will complete the cognitive function test via the CBS portal. The pseudoanonymised data will be held by CBS on a secure system and transferred to MEMO Research via a secure API.

The eCFR will be the web profile with different levels of access. Access level will be role specific.

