7.4 TRANSFER OF DATA

No patient data will be removed by the study team from GP practices. All data will be entered on the study web portal directly by participants using either unique links sent to personal validated email addresses, or username and password login.

Cambridge Brain Science (CBS) are fully GDPR compliant. Their application is hosted and managed entirely by CBS and is not installed outside of the CBS infrastructure. They require no patient identifiable information to analyse the cognitive assessments. A unique CBS code will be generated for each participant by the RECALL Pilot website and this code will be used to generate all links to CBS. Participants will carry out the online cognitive function tests and CBS will send us the scores against the participants CBS code. Only MEMO Research will hold the link between the CBS code and an identifiable patient.

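### As worded, the i-STAT feasibility outcome takes blood results as its denominator, so it reads 100% whatever the losses; it should count consented participants

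*Protocol*

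**What the plan says.** Protocol section 3, Table 2, sets the secondary objective "Assess feasibility of using portable i-STAT Alinity device for providing blood results" and gives it one outcome measure: "Proportion of blood results obtained using portable system". The synopsis repeats both.

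The route to a blood result is described in four places:

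- Section 4.1.4: "Participants will be asked to have a blood test carried out using the i-STAT Alinity portable system developed by Abbott", and "The blood test will involve one draw of venous blood".
- Section 4.5: "One blood sample will be collected, analysed and discarded at the same visit in this study".
- Section 6.1: "Research Nurses will enter the results of the blood test taken using the i-STAT Alinity Device".
- Section 7.4: "No patient data will be removed by the study team from GP practices".

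Section 5.5, on COVID-19, widens the choice of venue ("allow the use of community hubs or other suitable facility for taking blood samples") and accepts delay. It does not change the device.

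The other six rows of Table 2 are proportions of participants, of the study population or of those invited. The i-STAT row alone is a proportion of results.

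**The concern.** A feasibility proportion is useful only if failures stay in its denominator. Here the denominator named is blood results. A participant who never attends, a draw that fails or an analyser error produces no blood result, so none of these would enter either part of the fraction.

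Obtaining blood results on the portable device is one of the components that section 4.1 lists for testing, and this is the only outcome tied to that objective. Section 7.2 says that the descriptive statistics for each outcome will support planning of the large randomised trial. A figure fixed at 100% would give that planning no information and could be mistaken for evidence that the device works well in this setting. Losses are foreseeable: section 5.5 itself anticipates delayed samples and participants who would rather avoid a hospital visit.

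**Working it through.** The protocol states no expected value or target for this outcome and no formal sample size calculation (section 7.1), so there is no figure to reproduce. The check is on the definition.

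**Step 1: sources of blood results.** Section 4.1.4 gives the i-STAT as the means of testing, from a single draw. Section 4.5 has that one sample analysed and discarded at the visit, which leaves nothing for a laboratory. Section 6.1 describes entry of i-STAT results and no other blood data. Section 7.4 rules out extraction from practice records. No laboratory comparator or fallback appears anywhere.

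**Step 2: the ratio as worded.** Let R be the number of blood results and R_p the number obtained on the portable system. With the i-STAT as sole source, R_p = R, so R_p/R = 1 for any R > 0. Section 4.1.4 lists twelve values, and the protocol does not say whether a result means a panel or a single value. The ratio is 1 in either case.

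**Step 3: comparison with informative denominators.** Let N be consented participants and A be attempted tests. The alternatives are R/A and R/N. I take N = 100, the planned minimum in section 7.1. Attendance of 40–100% and success of 80–100% per attempt are assumptions, not protocol figures. Intervals are exact (Clopper-Pearson) 95%.

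| N | A | R | As worded, R/R | Per attempt, R/A (95% CI) | Per consented, R/N (95% CI) |
|---|---|---|---|---|---|
| 100 | 100 | 100 | 100% | 100% (96.4–100) | 100% (96.4–100) |
| 100 | 100 | 80 | 100% | 80% (70.8–87.3) | 80% (70.8–87.3) |
| 100 | 80 | 80 | 100% | 100% (95.5–100) | 80% (70.8–87.3) |
| 100 | 80 | 64 | 100% | 80% (69.6–88.1) | 64% (53.8–73.4) |
| 100 | 40 | 32 | 100% | 80% (64.4–90.9) | 32% (23.0–42.1) |

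The figure as worded never moves. Per consented participant, the same data run from 32% to 100%.

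**Step 4: why a second figure helps.** Rows two and three both give 80% per consented participant. In row two every participant attends and a fifth of tests fail; in row three a fifth do not attend and every test works. Only the per-attempt figure (80% against 100%) tells them apart, and the objective is about the device.

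**The case against.** The best defence is that the table cell is elliptical. The objective beside it concerns providing blood results, section 4.1 lists obtaining results on the device as a component under test, and each participant is asked for one test. On that view the cell means the share of requested results that were actually obtained, which is informative. The analysis plan promised in section 7.2, which is not shown, may say so, and section 7.3 leaves missing data to it.

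This stands in part. The looser reading is possible and may be what was meant. But the protocol nowhere states a denominator of requested or expected results for this row. The one it names makes the outcome uninformative, while the parallel home blood pressure row counts participants. This is therefore a denominator worded badly, not a detail merely left to the analysis plan. An analysis plan could repair it only by replacing the wording.

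Two stronger inferences are tempting, and the documents do not support them:

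- *The objective cannot be answered at all.* Consent is recorded for every participant (section 5.2) and i-STAT results are entered (section 6.1), so results per consented participant can be computed from data already planned. Feedback questionnaires for those who have not completed sections (section 4.1.6) may add some explanation. The undefined primary measure of protocol adherence might also touch on it, but does not separate device failure from non-attendance.
- *Failed attempts will go unrecorded.* Section 6.1 says that nurses enter results. It does not say that failures are omitted, and the eCRF is not shown.

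**Conclusion.** The point holds as a matter of wording. Read literally, and with the i-STAT as the only source of blood results, the outcome equals 100% at any level of attendance or device failure and cannot return an unfavourable answer. The conclusion rests on that literal reading and on the absence of any other blood-result route, which sections 4.1.4, 4.5, 6.1 and 7.4 support and no section contradicts. The percentages in the table are illustrations under assumed attendance and success. They show how far the figure could mislead, not a bias that has occurred.

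Its weight is moderate. This is one of seven secondary outcomes in a descriptive study. The protocol attaches no threshold or progression decision to it, and the objective can still be answered from planned data. A reader might infer that the study is compromised on this component. It is not: the stated statistic is uninformative, but the underlying data are sufficient for a better one.

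**What to change.** Reword the outcome in the synopsis and in Table 2 so that it reads, for example: *proportion of consented participants for whom a blood result was obtained on the i-STAT*. This brings the row into line with the home blood pressure row and uses data already collected.

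Where attempts are recorded, also report the proportion of attempted i-STAT tests that gave a valid result, so that failure at testing can be told apart from non-attendance. If the eCRF does not already hold this, it needs one extra field for attempts.

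The cost is two table cells, possibly that field, and a reported figure that will probably be less favourable than 100%. No study procedure changes. A first-attempt success measure, a classification of the reasons for loss and a breakdown by venue are optional. With about 100 participants, a breakdown by both cause and venue would leave very small cells.

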4 STUDY DESIGN

Cohort feasibility study.

4.1 INTERVENTION

Components of the proposed formal study methodology for recruitment and baseline data collection will be tested including:

- Online registration and consent procedures
- Online cognitive function testing
- Home blood pressure submission
- Bloods results obtained using portable i-STAT Alinity device
- Participant feedback questionnaires

4.1.1 Online registration and Consent

See section 5.2

4.1.2 Online Cognitive Testing

Cognitive testing will be performed by Cambridge Brain Sciences (CANADA), a well-established provider of online cognitive testing with a custom-built research platform (http://www.cambridgebrainsciences.com/).

All transaction between MEMO Research and CBS will be end-to-end encrypted via the use of HTTPS and SSL certificates. The only data sent from MEMO Research to CBS will be an anonymous locally generated patient identifier. CBS will return the results of the tests via an encrypted API to MEMO Research along with the anonymous patient identifier. Only MEMO Research will be able to map results to the study participants.

4.1.3 Home Blood Pressure Submission

Consenting participants will be provided with a home blood pressure monitor and instructions for use. They will be invited to submit a baseline set of home readings (modified version of NICE guidance on HBPM for diagnosis of hypertension) [1] via a unique emailed link or by logging in to their study homepage.

4.1.4 Blood Tests

Participants will be asked to have a blood test carried out using the i-STAT Alinity portable system developed by Abbott. This sample will be obtained at either the GP practice, MEMO Research at Ninewells Hospital, a Community hub or other suitable facility (investigator opinion) as necessary. The blood test will involve one draw of venous blood and will provide results for: Sodium, Potassium, Chloride, TCO2, Anion Group, Ionized Calcium, Glucose, Urea Nitrogen (BUN), Creatinine, calculated eGFR, Haematocrit and Haemoglobin

Full working instructions and training will be provided to the Health Care Professional using the i-STAT system.

4.1.5 Alternative Contacts

Consented participants will be asked to provide the email addresses of two alternative contacts (relative, family friend or carer) who can be contacted if the study team are unable to contact the participant. The participant will be asked to seek agreement from their alternative contacts prior to them entering their details into the RECALL secure website. Alternative contacts will be asked by email to confirm that they are willing to act in this capacity and to verify their email address. If any alternative contacts select not to agree to this provision on the website, the participant will be asked to provide a further contact. Although participants will be requested to provide two alternative contacts, if they cannot provide this, they can still proceed into the study. Alternative contacts will only be emailed should contact with the participant be lost during the study.

4.1.6 Participant Feedback Questionnaires

[figure not shown]
Participants will be given the opportunity to complete a feedback questionnaire after finishing each section of the study on-line. Questionnaires will also be presented to participants at the end of the trial if they have not completed sections, or if they withdraw from the study.

4.2 STUDY DESCRIPTION

Potential participants will be invited to visit a study web page by letter of invitation. On this study webpage they can read the participant information documentation and then complete an electronic informed consent form. Participants will then be asked to complete questions on their demographics, medical history, and lifestyle.

Consenting participants will be supplied with a home blood pressure monitor (HBPM) and detailed instructions on how to use it. They will then be asked to submit a set of readings (modified version of NICE guidance) [1].

4.3 STUDY FLOWCHART

4.4 STUDY SAFETY ASSESSMENTS

No Investigational Medicinal Produce (IMP) will be used in this feasibility study. Study procedures will involve direct participant data entry, online cognitive function testing and home blood pressure monitoring. All of these have been previously undertaken in other situations without significant safety concerns [2,3].

4.5 TISSUE

One blood sample will be collected, analysed and discarded at the same visit in this study.

4.6 INCIDENTAL FINDINGS

Any incidental findings (e.g. previously undiagnosed condition) considered to be clinically significant will be reported to the participant's GP by the CI with the consent of the participant.

